5.5.9 Discontinuation of study treatment

Permanent discontinuation of LCZ696 constitutes withdrawal from the study. Under these circumstances, the patient should be evaluated at a final study visit but will not undergo assessments thereafter unless additional follow-up is required due to prior occurrence of an adverse event.

The investigator must also notify the IRT of the patient's discontinuation of LCZ696 and record it on the Drug Administration Record of the eCRFs.

The emergence of the following circumstances will require study drug discontinuation:

- Withdrawal of informed consent
- Pregnancy ([Section 6.5.6](#) and [Section 7.6](#))
- Investigator thinks that continuation would be detrimental to the patient's well-being

Study medication may be discontinued at the investigator's discretion if any of the following occurs:

- Any severe suspected drug-related AE
- Suspected occurrence of angioedema. A patient with any signs or symptoms of clinically significant angioedema should be thoroughly evaluated by the investigator and constitute a reason for discontinuation of study medication.

Depending on the serum potassium, blood pressure, or eGFR, patients may need to have their LCZ696 dose or the dose of another concomitant medication reduced or discontinued, or, if appropriate, have potentially contributing agents adjusted. Please refer to [Appendix 3](#), [Appendix 4](#) and [Appendix 5](#) for treatment guidelines for hyperkalemia, hypotension, or renal dysfunction, respectively.

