7.4 Serum potassium safety monitoring (hyperkalemia)

To ensure patient safety, a standardized process for identifying, monitoring, and managing hyperkalemia is summarized in [Appendix 3](#).

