> 3 x ULN	Medically significant	Repeat LFT within 48 hours If elevation persists, discontinue the study drug immediately Hospitalize if clinically appropriate Report to Novartis as an SAE Establish causality	ALT, AST, TBL, Alb, PT, ALP and γ GT until resolution ^c (frequency at investigator discretion) Test for hemolysis (e.g., reticulocytes, haptoglobin, unconjugated [indirect] bilirubin)
> 1.5 to \leq 3 x ULN	AESI	Laboratory to report to	investigator discretion

Criteria	Event type	Actions required	Follow-up monitoring
(patient is asymptomatic)		Investigator and Investigator to Novartis Repeat LFT once or twice in the week. If elevation persists, establish causality	Monitor LFT within 1 to 4 weeks or at next visit
≤ 1.5 x ULN (patient is asymptomatic)	N/A	Repeat LFT at next visit	
Preferred terms			
Jaundice	Medically significant	Discontinue the study drug immediately Hospitalize the patient Report to Novartis as an SAE Establish causality	ALT, AST, TBL, Alb, PT, ALP and γGT until resolution ^c (frequency at investigator discretion)
“Drug-related hepatic disorders - severe events only” SMQ AE	Medically significant	Discontinue the study drug Hospitalization if clinically appropriate Report to Novartis as an SAE Establish causality	Investigator discretion

^a Elevated ALT/AST > 3 x ULN and TBL > 2 x ULN but with no notable increase in ALP to > 2 x ULN

^b General malaise, fatigue, abdominal pain, nausea, or vomiting, rash with eosinophilia

^c Resolution is defined as an outcome of one of the following: return to baseline values, stable values at three subsequent monitoring visits at least 2 weeks apart, remain at elevated level after a maximum of 6 months, liver transplantation, and death.

15 **Appendix 3: Treatment guidelines for hyperkalemia (serum potassium greater than or equal to 5.3 mmol/L)**

General principles

Elevation of potassium levels above the predefined values should be repeated and confirmed before any action is taken.

Any patient with a serum potassium > 5.3 mmol/L after enrollment into the study requires regular, repeated checks of potassium concentration (beyond that prescribed in the protocol) until it is clear that the potassium concentration is stable and not rising into the range of concern (≥ 5.5 and < 6.0 mmol/L) or potential danger (≥ 6.0 mmol/L).

Patients with an elevated potassium value will be managed according to the corrective actions outlined below. Hyperkalemia should be followed until resolution.

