Corrective action for management of hyperkalemia

Serum potassium > 5.3 and less than or equal to 5.5 mmol/L

- Confirm potassium concentration in a non-hemolyzed sample
- Reinforce low potassium diet and restriction of food/drinks with high potassium content (e.g. orange juice, melon, bananas, low-salt substitutes etc.)
- Review medical regimen (including dietary supplements and over-the-counter medications) for agents known to cause hyperkalemia. Consider reduction in dose or discontinuation of these agents:
 - Aldosterone antagonists (if they are believed to be the most likely cause of hyperkalemia)
 - Potassium-sparing diuretics (e.g. amiloride and triamterene) including in combination products with thiazide or loop diuretics
 - Potassium supplements, e.g., potassium chloride
 - Salt substitutes
 - Non-steroidal anti-inflammatory drugs (NSAIDs)
 - Cyclo-oxygenase-2 (COX-2) inhibitors
 - Trimethoprim and trimethoprim-containing combination products, such as Bactrim® and Septra® (trimethoprim/sulfamethoxazole fixed combination)
 - Herbal Supplements:
 - For example, Noni juice, alfalfa (*Medicago sativa*), dandelion (*Taraxacum officinale*), horsetail (*Equisetum arvense*), nettle (*Urtica dioica*), milkweed, lily of the valley, Siberian ginseng, hawthorn berries
 - Repeat serum potassium measurement within 3 to 5 days
 - If serum potassium remains > 5.3 and ≤ 5.5 mmol/L, regularly monitor serum potassium levels to ensure stability (suggested once monthly)

- Consider down-titration of study medication, according to investigator's medical judgment.

Serum potassium > 5.5 and < 6.0 mmol/L

- Confirm potassium concentration in a non-hemolyzed sample
- Consider down-titration or temporarily discontinue study drug according to investigator medical judgment.
- Apply all measures outlined for serum potassium > 5.3 and \leq 5.5 mmol/L
- Repeat serum potassium measurement after 2-3 days
- If serum potassium < 5.5 mmol/L, consider resumption of study drug at lower dose with repeat potassium within 5 days

Serum potassium greater than or equal to 6.0 mmol/L

- Immediately discontinue study drug
- Confirm potassium concentration in a **non-hemolyzed sample**
- Urgently evaluate patient and treat hyperkalemia as clinically indicated
- Apply all measures outlined for serum potassium > 5.3 and < 6.0 mmol/L

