Notification to the sponsor of a potassium level equal to- or above 6 mmol/L should be done within 48 h. No resumption of study drug without individualized case discussion with and permission from the Sponsor's Medical Monitor or his/her designee.

16 Appendix 4: Guidelines for the management of blood pressure

Guidelines

1. Investigator should monitor blood pressure closely
2. If symptomatic hypotension occurs:
 - a. Correct any treatable cause, e.g. hypovolemia
 - b. If hypotension persists, any antihypertensive drug and non-disease-modifying drugs, such as diuretics, CCBs, nitrates, and α -blockers, should be down-titrated or stopped first before down-titration of the study drug is considered

If hypotension persists, the study drug should be down-titrated or even temporarily withdrawn. The dose re-challenge and medication adjustment guidelines described in [Section 5.5.5](#) should be adhered to as much as possible.

17 **Appendix 5: Guidelines for the management of renal dysfunction**

General principles:

Glomerular filtration rate in HF patients depends on intrinsic renal function and on a balance between afferent and efferent glomerular arterial tonicity. This tonicity is partly regulated by a stimulation of angiotensin II and could be affected by study medication. Moreover, renal dysfunction may develop or may deteriorate in some patients after study drug administration. The recommendations that follow have been developed to guide investigators in managing patients with renal dysfunction during the course of the study.

Two types of response to serum creatinine increase are described:

Surveillance situation

If, at any time after enrollment, eGFR decreases by $\geq 25\%$ from baseline (Visit 1) (or if serum creatinine concentration increases to 2.5 mg/dL [221 $\mu\text{mol/L}$]), the investigator will check for potentially reversible causes of renal dysfunction such as:

- Non-steroidal anti-Inflammatory drug intake, antibiotics, or other treatments known to affect creatininemia
- Volume decrease, including that resulting from excessive dosing of diuretics
- Urinary infection
- Urinary tract obstruction
- Study medication

Action situation

If a patient eGFR decreases by $\geq 40\%$ from baseline (Visit 1) (or if serum creatinine concentration rises above 3 mg/dL (265 $\mu\text{mol/L}$), the investigator will check for potentially reversible causes of renal dysfunction (see above).

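### Protocol Appendix 3 gives two opposed orders of stopping and confirming for an unconfirmed potassium reading of 6.0 mmol/L or above

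*Protocol*

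**What the plan says.** Protocol Appendix 3 has a block of general principles followed by three action tiers. The general principles state: "Elevation of potassium levels above the predefined values should be repeated and confirmed before any action is taken". They go on to name the top range as one of "potential danger (≥ 6.0 mmol/L") and make no exception for it. They also link forward to the tiers: "Patients with an elevated potassium value will be managed according to the corrective actions outlined below".

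The tier for 6.0 mmol/L and above begins "Immediately discontinue study drug". Its second bullet is "Confirm potassium concentration in a" non-hemolyzed sample. Urgent evaluation follows, together with all measures from the lower tiers. The text after the tier requires the sponsor to be told within 48 h and adds: "No resumption of study drug without individualized case discussion with and permission from the" sponsor's Medical Monitor or a designee.

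The body of the protocol relies on this appendix. Section 7.4 reads: "To ensure patient safety, a standardized process for identifying, monitoring, and managing hyperkalemia is summarized in" Appendix 3. Section 5.5.9 says "Depending on the serum potassium, blood pressure, or eGFR, patients may need to have their LCZ696 dose" or another drug's dose reduced or discontinued, and again refers to the appendix.

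**The concern.** Stopping study drug is an action. If an elevation has to be confirmed before any action, a single reading of 6.0 or above does not yet permit a stop. If drug has to be stopped immediately, the stop cannot wait for the repeat. A site holding one unconfirmed reading has both instructions in the same appendix.

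This is a stopping instruction in the range that the protocol itself marks as most dangerous. Hyperkalemia is a named study risk (section 3.6) and an adverse event of special interest (section 9.4). Samples are analyzed locally (section 6.5.4) and there is no Data Monitoring Committee (section 8.4), so sites depend heavily on the written instruction.

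The order may also affect what follows. A site that confirms first and finds a lower value would not have stopped under this tier. A site that stops first may then fall under the rule requiring Medical Monitor permission to resume, even if the repeat does not confirm the value. The text does not say whether that rule applies in such a case.

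**Working it through.** No arithmetic applies, and the plan gives no figure to reproduce. The check compares the general principle with each tier, then looks for a sentence elsewhere that settles the order.

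**Step 1. General principle against each tier of Appendix 3**

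| Tier (mmol/L) | First bullet | Where confirmation stands | Agrees with confirm-first? |
|---|---|---|---|
| > 5.3 to ≤ 5.5 | Confirm in a non-hemolyzed sample | First | Yes |
| > 5.5 to < 6.0 | Confirm in a non-hemolyzed sample | First; down-titration or temporary stop follows, at the investigator's judgment | Yes |
| ≥ 6.0 | Stop study drug at once | Second | No |

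Two of three tiers agree with the general principle and one does not. The bullets are unnumbered, so their order alone would be weak evidence. The conflict does not depend on it: an immediate stop is incompatible with confirming before any action, whatever the order of the list.

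**Step 2. Does the top tier apply only to values already confirmed?** The tier does not say so. If it did apply only to confirmed values, its own instruction to confirm would be redundant. The tier also imports the measures of the two lower tiers, each of which starts with confirmation.

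**Step 3. Does another section set the order?** Five body sections refer to Appendix 3 for potassium or hyperkalemia: 5.1.1, 5.5.5, 5.5.6, 5.5.9 and 7.4. None of the five states an order of confirming and stopping. Two other sentences bear on the question:

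- The linking sentence in the general principles sends patients to the tiers. It favours the tier, but it stands beside the confirm-first sentence and does not suspend it.
- Section 11.1 expects investigators to act at once where a patient's safety requires it, even if that deviates from the protocol. It permits a stop; it does not say which potassium instruction is the protocol's rule.

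**Step 4. Can the protocol state such an order elsewhere?** Yes. In Table 14-2 (liver events), the row for ALT or AST above 8 x ULN calls for a repeat within 48 hours and a stop if the elevation persists. The row for a potential Hy's Law case calls for an immediate stop with no repeat step before it. Each row gives one order. Appendix 3 gives two for its top tier.

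**Step 5. Could the affected cases be counted?** The documents give no rate of readings at or above 6.0 and no rate of readings that fail to confirm. Section 8.3 keeps potassium values in source documents and out of the clinical database. Some cases would still leave a trace: dose changes and withdrawals are recorded in the eCRF and IRT (section 5.5.5), action taken is recorded for each adverse event (section 7.1), and levels of 6.0 or above are notified to the sponsor (Appendix 3). These records would give a partial list to check against source. None is described as recording whether the stop preceded the confirmation.

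**The case against.** The strongest case on the other side is that the text has a natural resolution. The general principle is worded as a recommendation, the appendix is titled as guidelines, and section 5.5.6 calls it guidance. The linking sentence hands management to the tiers, and a specific instruction to act at once is ordinarily read as governing its own range. Section 11.1 also means that confirm-first cannot hold back an investigator who judges a stop necessary for safety. Many investigators would probably follow the tier.

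Much of this stands, and it lowers the severity. It does not remove the inconsistency. Advisory wording still gives a site two opposite pieces of advice, and the rule that the specific overrides the general is not written in the protocol. Section 11.1 treats the immediate act as a possible deviation, so it does not tell a site which course is the compliant one.

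A reader might draw three stronger conclusions that the documents do not support:

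- **That management at 6.0 and above is not standardized at all.** The threshold, discontinuation, confirmation, urgent evaluation, the lower-tier measures and the 48 h notification are fixed. Only the order of stopping and confirming is open.
- **That a site which stops first must obtain permission to restart after a repeat that does not confirm the value.** The permission rule may apply there, but the text does not say.
- **That the study records could not reveal any case.** Potassium values are absent from the clinical database, but dose-change, adverse event and sponsor-notification records would identify some cases.

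**Conclusion.** Appendix 3 is internally inconsistent for an unconfirmed potassium reading of 6.0 mmol/L or above. The conflict lies in one of three tiers and concerns only whether drug is stopped before or after confirmation. No sentence in the protocol says which instruction prevails, although the linking sentence leans towards the tier.

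The number of patients affected cannot be sized from the documents, and no estimate is offered. A reader might infer that the safety results are materially distorted. The documents do not support that. An abnormal value becomes an adverse event only under the criteria in section 7.1, so the section 9.4 counts of adverse events leading to interruption or discontinuation could shift only through cases recorded on that basis. Section 9.7 of the protocol states that no specific sample size is required and no treatment comparison is planned, so no sample size or error rate is touched.

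The conclusion rests on reading stopping drug as an action within the meaning of the general principle, and on the absence of any precedence rule in the protocol. It is a should-fix matter of internal consistency: relevant to safety and cheap to repair, but not a threat to the analysis.

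**What to change.** The sponsor should reconcile the general principle in Appendix 3 with the tier for 6.0 mmol/L and above so that a single order of stopping and confirming applies to a first, unconfirmed reading, and should state that order in both places. Which order is right is for the sponsor's clinicians; this review proposes none.

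The cost is about one sentence in each of two places, made by protocol amendment with notification to sites. No new procedure, assessment or data field is needed, and the SAP does not change.

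### Protocol Appendix 3: the potassium limits disagree at exactly 5.3 and exactly 5.5 mmol/L

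*Protocol*

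**What the plan says.** Appendix 3 states its potassium limits in three places.

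- **Title**, repeated in the table of contents: "Treatment guidelines for hyperkalemia (serum potassium greater than or equal to 5.3 mmol/L". The value 5.3 is included.
- **General principles.** The extra-check rule reads "Any patient with a serum potassium > 5.3 mmol/L after enrollment into the study requires regular, repeated checks", so 5.3 is not included. The checks go on until potassium is stable and "not rising into the range of concern (≥ 5.5 and < 6.0 mmol/L", so 5.5 is included in that range. A value of 6.0 or more is labelled potential danger. This part also says: "Hyperkalemia should be followed until resolution".
- **Corrective action.** The first tier is headed "Serum potassium > 5.3 and less than or equal to 5.5 mmol/L". The second runs from above 5.5 to below 6.0, and the third starts at 6.0.

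The first tier says "Repeat serum potassium measurement within 3 to 5 days" and asks the investigator to consider down-titration. The second says "Repeat serum potassium measurement after 2-3 days" and asks the investigator to consider down-titration or temporary discontinuation. The second tier's restart rule is "If serum potassium < 5.5 mmol/L, consider resumption of study drug at lower dose".

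Protocol Sections 5.5.5, 5.5.9 and 7.4 send investigators to this appendix, and Section 7.4 presents it as a standardized process.

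**The concern.** Laboratories are local and sites act on the written limits, so one potassium result should lead to one reading of the appendix. At 5.3 a site that goes by the title would expect guidance and find none, because the trigger and every tier exclude that value. Scheduled visits are six months apart after Visit 5 (Section 5.5.4), so whether a 5.3 prompts an extra check matters somewhat to the individual patient. At 5.5 the General principles name a level of worry that the corrective actions do not match: the result gets the lower tier's later recheck and no listed prompt to interrupt. Hyperkalemia is one of the adverse events of special interest (Protocol Section 9.4), so it is worth having these limits agree.

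**Working it through.** No sample size, power or error rate bears on this point. The check is to apply every stated limit to each value in turn. Results are taken to one decimal, an assumption that matches the cut-offs in the text.

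| Potassium, mmol/L | Title (≥ 5.3) | Extra-check trigger (> 5.3) | Label in General principles | Action tier | Restart limit (< 5.5) met |
|---|---|---|---|---|---|
| 5.2 | no | no | none | none | yes |
| **5.3** | **yes** | **no** | none | **none** | yes |
| 5.4 | yes | yes | none | first | yes |
| **5.5** | yes | yes | **range of concern** | **first** | no |
| 5.6 to 5.9 | yes | yes | range of concern | second | no |
| 6.0 and above | yes | yes | potential danger | third | no |

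Only 5.3 and 5.5 are out of line. No value falls in two tiers.

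**What still applies at 5.3.**
- Section 6.5.4 has the investigator review all results, asks for flags on values outside the normal range and on notable values, and schedules potassium at every visit.
- Section 5.5.7.2 encourages regular potassium checks.
- Appendix 3 itself asks for hyperkalemia to be followed to resolution.
- Appendix 1 makes a rise of more than 20% from baseline notable. A value of 5.3 meets this only if baseline was below 5.3 / 1.2 = 4.42. For example, 4.4 × 1.2 = 5.28 is below 5.3, so it is notable; 4.5 × 1.2 = 5.40 is above 5.3, so it is not. Exclusion criterion 9 admits baselines up to 5.2, so the Appendix 1 rule alone does not cover everyone at 5.3. The local normal-range flag may cover the rest, but the documents do not give those ranges.

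**What differs at 5.5.** The recheck windows share day 3. Their outer limits are day 5 (first tier) and day 3 (second tier), a difference of 5 − 3 = 2 days. Both tiers ask for a confirmatory non-hemolyzed sample and for down-titration to be considered. Temporary discontinuation is listed only in the second tier.

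**With the preferred limits**, 5.3 meets the title, the trigger and the first tier. The value 5.5 is in the range of concern and the second tier, and fails the restart limit, all in agreement. **With the minimal alternative**, 5.3 is outside the title, trigger and tiers, and 5.5 is in the first tier and outside the range of concern.

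**The case against.** The strongest reply is that this is a proofreading matter. Range of concern is a label with no action attached, and the tier headings give 5.5 exactly one set of actions. At 5.3, Appendix 3 says that patients with an elevated value are managed by the corrective actions, so under a title that includes 5.3 a site would naturally use the mildest tier. Drug changes below 6.0 are discretionary, and Section 5.5.9 allows reduction or discontinuation according to serum potassium.

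Much of this stands. Action at 5.5 is uniquely assigned, so it would be wrong to infer that the appendix gives two competing instructions there. It would also be wrong to infer that a patient at 5.3 goes unflagged or unfollowed, given the general provisions above. The restart limit of below 5.5 might be read as a third error, but a restart rule slightly stricter than the interruption threshold is coherent.

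What does not stand is that the text needs no change. Placing 5.3 in the mildest tier contradicts that tier's own heading, and a site that follows the heading has no listed step. At 5.5 the label and the tier still disagree about how serious the value is. The screening exclusion of values above 5.2 fits a limit of ≥ 5.3 at one decimal, which hints at the intended bound but does not prove it.

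**Conclusion.** Two boundary mismatches stand in the current text of Appendix 3. Exactly 5.3 is in the title but outside the extra-check trigger and all tiers. Exactly 5.5 is in the range of concern but managed in the lower tier. The consequence is limited to possible extra checks at 5.3 and, at 5.5, a recheck whose outer limit is 2 days later with no listed prompt to interrupt. The priority is low.

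The frequency is unknown: the documents give no potassium distribution, so no count of patients is offered. If laboratories report more than one decimal, the mismatches remain but are met less often.

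A reader might infer that the mandatory stop at 6.0 is affected. Its bound is the same wherever it is stated. The one difference there is the order of steps: the General principles ask for confirmation before any action, while the third tier lists stopping the drug before confirming. That is separate from the limits.

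A reader might also infer that a planned result would change. Local laboratory values are not entered in the clinical database (Protocol Section 8.3), and the primary safety evaluation uses adverse events and vital signs (SAP Section 9.7.1.6), so no planned analysis changes.

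**What to change.** **Preferred, as the more cautious.** Keep the title, the range of concern and the restart limit. Make seven edits in Appendix 3:

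1. Extra-check trigger: ≥ 5.3.
2. First-tier heading: ≥ 5.3 to < 5.5.
3. First-tier bullet on potassium that remains raised: same limits as the heading.
4. Second-tier heading: ≥ 5.5 to < 6.0.
5. Cross-reference in the second tier: ≥ 5.3 to < 5.5.
6. Cross-reference in the third tier: ≥ 5.3 to < 6.0.
7. Opening sentence of the General principles on repeating and confirming elevations: make it apply to values at or above the predefined limits, since it now says only above.

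**Minimal alternative.** Make three edits: title and contents entry to > 5.3, and range of concern to > 5.5 and < 6.0. Leave the tiers and the < 5.5 restart limit as they are.

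The sponsor's clinical team should confirm which limits were intended. The preferred version costs a few extra potassium tests at 5.3 and earlier ones at 5.5. It also adds discretionary prompts: to consider down-titration at 5.3 and interruption at 5.5. The alternative adds no tests. Either could go into an administrative amendment.
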